For patients discharged from outpatient care, data sources will be checked for any readmissions/rescans thought to be attributed to the incidental meningioma within the study timeframe; date of diagnosis up to the date of data entry. Outcome following readmissions/rescans will be noted.

Grade I	Any non–life-threatening deviation from normal postoperative course, not requiring invasive treatment
Grade Ia	Complication requiring no drug treatment
Grade Ib	Complication requiring drug treatment
Grade II	Complication requiring invasive treatment such as surgical, endoscopic, or endovascular interventions
Grade IIa	Complication requiring intervention without general anaesthesia
Grade IIb	Complication requiring intervention with general anaesthesia
Grade III	Life-threatening complications requiring management in ICU
Grade IIIa	Complication involving single organ failure
Grade IIIb	Complication involving multiple organ failure
Grade IV	Complication resulting in death
Surgical Complications	Adverse events that are directly related to surgery or surgical technique
Medical Complications	Adverse events that are not directly related to surgery or surgical technique
Suffix “T” (Transient)	New neurologic deficit improving within 30 days of surgical procedure; can be added to each grade of complication
Suffix “P” (Persistent)	New neurologic deficit extending beyond 30 days of surgical procedure; can be added to each grade of complication

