Two competing risk analyses will be performed. One assessing the cumulative incidence rate (CIR) of primary intervention at different time points following diagnosis stratified by PS and ACCI groups and the other will evaluate the CIR of disease progression. The competing event for the former will be non-meningioma-specific mortality either observed during follow-up or after being discharged from outpatient care. Patients who remain under follow-up will be censored at the last outpatient clinic appointment. Patients discharged alive from outpatient care will be censored at the last time they were seen by a healthcare physician up to the date of data entry.

For the disease progression analysis, mortality after hospital discharge could not be used as a competing event as the time interval between discharge and death could have seen radiological changes which meet the disease progression definition. Instead, four events will

be considered competing in nature, discharge from outpatient care, loss to follow-up, death during follow-up or an intervention before disease progression occurred with the first three grouped together. Censoring will only be done for patients who remain under follow-up at the last clinic appointment. To test the equality across CIR groups, the Fine and Gray test will be carried out. Plots of CIRs and 95% confidence intervals (CIs) will also be generated and compared to the training data set (11).

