Rescanned during the time between discharge/loss to FU and the date of data entry	Checkbox	Required entry
Date of scan	DD/MM/YYYY	Prompt entry if previous option (Readmitted/rescanned during the time between discharge/loss to FU and the date of data entry) has been checked
Reason?	Dropdown list: 
 • Seizure • Headache • Motor • Sensory • Language • Cognitive 	Prompt entry if previous option (Readmitted/rescanned during the time between discharge/loss to FU and the date of data entry) has been checked. Allow multiple options

	
 • Other 	
Peritumoural signal intensity on T2	Dropdown list/check box 
 • 0-5% • 6-33% • 34-66% • 67-100% • NA 	Prompt entry if previous option (Readmitted/rescanned during the time between discharge/loss to FU and the date of data entry) has been checked. Allow one option only Note to data collector: In relation to tumour volume. If only baseline CT available, NA
Peritumoural signal intensity on FLAIR	Dropdown list: 
 • 0-5% • 6-33% • 34-66% • 67-100% • NA 	Prompt entry if previous option (Readmitted/rescanned during the time between discharge/loss to FU and the date of data entry) has been checked. Allow one option only Note to data collector: In relation to tumour volume. If only baseline CT available, NA
Venous sinus nearby	Checkbox 
 • Superior sagittal sinus • Cavernous sinus • Sigmoid sinus • Transverse sinus • Confluence of sinuses 	Prompt entry if previous option (Readmitted/rescanned during the time between discharge/loss to FU and the date of data entry) has been checked Note to data collector: Tick box if within 10 mm, in direct contact or invading one of: superior sagittal sinus (SSS), sigmoid sinus (SS), transverse sinus (TS), cavernous sinus (CS) and the confluence of sinuses (CoS)
If yes, specify	Dropdown list/check box	Prompt entry if previous option (venous sinus nearby) has been ticked. Allow one option only
Separate, direct contact or invaded?	Dropdown list/check box 
 • Separate • Direct contact • Invaded 	Prompt entry if previous option (venous sinus nearby) has been ticked. Allow one option only

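### The PS/ACCI progression analysis codes discharge and loss to follow-up as competing events, so it estimates progression before monitoring ended, not the risk of progression, and differences in discharge distort its group comparisons

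*Protocol*

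**What the plan says.** Section 3.10.1 sets out to assess how age, comorbidity and PS affect the risk of progression. For the cumulative incidence of progression, the section names four outcomes that are to "be considered competing in nature, discharge from outpatient care, loss to follow-up, death during follow-up or an intervention before disease progression occurred". Discharge, loss and death are pooled into a single category. The censoring rule is explicit: "Censoring will only be done for patients who remain under follow-up at the last clinic appointment". Discharged and lost patients are therefore not censored.

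Just before this, the section explains why a later death is not used: "mortality after hospital discharge could not be used as a competing event as the time interval between discharge and death could have seen radiological changes" that would meet the definition of progression. The companion analysis of intervention handles discharge differently: "Patients discharged alive from outpatient care will be censored at the last time they were seen by a healthcare physician".

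The study also looks for events after discharge. Section 3.8.3 says that "data sources will be checked for any readmissions/rescans thought to be attributed to the incidental meningioma within the study timeframe". Appendix 1 (Section/Page 9) has a field headed "Rescanned during the time between discharge/loss to FU and the date of data entry", which opens entries for oedema, sinus relation and tumour diameters.

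The curves are compared across PS and ACCI groups with the Fine and Gray test and set against the training data. Under Stage 4 of section 3.10.2, the PS/ACCI strata are adjusted until that test shows significant differences.

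**The concern.** A competing event is one after which the event of interest can no longer happen. Death qualifies. Discharge and loss to follow-up do not: the tumour is still there and can still grow, and only the observation stops. The protocol's reason for not using death after discharge, that progression may have come in between, is a reason to censor at discharge, not to count discharge as competing.

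A discharged patient coded this way stays in the Fine and Gray risk set as someone who will not progress. Two consequences follow. The cumulative incidence falls below the risk of progression. And if one group is discharged or lost faster than another, its curve is lower even when tumours progress at the same rate. At stake are the PS/ACCI comparison, the comparison with the training cohort, and any strata redrawn under Stage 4. Section 3.4 itself expects follow-up regimes and losses to vary.

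**Working it through.** **Inputs from the protocol.** Progression risk 10%, 100 events required, at least 1500 patients (3.4); significance at P < 0.05 (3.10.3). The plan's own figure reproduces: 100 / 0.10 = 1000 patients, then raised to 1500. No figure is given for the competing-risk analysis.

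**Assumptions.** The 10% has no stated time horizon and is taken here as a 10-year risk. Tests are taken as two-sided. Discharge/loss rates are not in the protocol, so ranges are shown. Hazards are constant.

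**Step 1: direction.** The planned quantity is P(progression by t and before discharge or loss). It cannot exceed P(progression by t), so the direction needs no assumption about rates.

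**Step 2: size in one group.** With progression hazard l = -ln(0.9)/10 = 0.01054 per year and competing hazard c,

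CIF(10) = l/(l+c) × [1 - exp(-10(l+c))].

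With discharge/loss as the only competing event and a fraction d discharged or lost by year 5, c = -ln(1-d)/5:

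| Discharged/lost by 5 years | 10-year CIF as planned | True risk |
|---|---|---|
| 10% | 9.0% | 10% |
| 20% | 8.1% | 10% |
| 30% | 7.2% | 10% |
| 50% | 5.5% | 10% |
| 70% | 3.9% | 10% |

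**Step 3: two groups with the same progression hazard.** Add death and intervention at 1% per year each, with discharge/loss at 5% or 20% per year:

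- c = 0.07: 0.01054/0.08054 × (1 - exp(-0.8054)) = 7.2%
- c = 0.22: 0.01054/0.23054 × (1 - exp(-2.3054)) = 4.1%
- c = 0.02 (death and intervention only): 0.01054/0.03054 × (1 - exp(-0.3054)) = 9.1% in both groups

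**Step 4: the test.** Simulation with 1500 patients, 20% of them in the frailer group, 10 years of follow-up, equal progression hazards, 10% deaths at 10 years in both groups, and 2000 runs. Percentage of runs rejecting equality:

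| Discharged/lost by 5 years, reference v frailer | Planned coding, 10% risk | Planned coding, 20% risk | Cause-specific log-rank, discharge/loss censored (10% / 20% risk) |
|---|---|---|---|
| 20% v 20% | 6.1 | 5.1 | 6.2 / 5.8 |
| 20% v 40% | 13.7 | 26.7 | 4.8 / 4.3 |
| 20% v 60% | 50.0 | 82.3 | 4.2 / 5.1 |
| 20% v 80% | 88.2 | 99.8 | 4.8 / 5.4 |

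Where discharge differs, nearly all rejections show less progression in the group discharged more. A second design (40% in the high-discharge group, 10% risk, rates as in Step 3) gave 78% at 5 v 20% per year, 21% at 5 v 10, and 9% at 5 v 7.5.

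**Step 5: a true difference.** With a hazard ratio of 1.5 for the frailer group, 15% base risk, discharge 20% v 60% by 5 years and deaths 10% v 40% at 10 years, the planned test rejected in 27% of runs, all in the wrong direction. Mortality differs here too, so discharge is not the only cause.

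**The case against.** The strongest defence is that the choice is deliberate. Progression before monitoring ends is an interpretable quantity, the introduction describes the model as concerning progression during active monitoring, and the same coding allows a like-for-like comparison with the training data. This stands as a reason to keep the analysis, but not under its present name. A quantity that depends on discharge practice can also differ from the training cohort when prognosis is the same.

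A reader might infer more than the documents support:

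- *That the PS/ACCI comparison mainly reflects who is discharged.* No discharge or loss rates by PS or ACCI are given, and nothing states that frail patients are discharged earlier. With equal discharge the test keeps its size, although the incidence is still too low. The highest rejection rates need a very large contrast: 20% per year means 63% discharged or lost by year 5 (1 - exp(-1)), against 22% at 5% per year (1 - exp(-0.25)).
- *That correcting the coding would make equal hazards give equal curves.* It would not if mortality differs. With no discharge at all, equal progression hazards and assumed death rates of 1 v 5, 8 or 12% per year, a Gray-type test rejects in 20%, 47% and 78% of runs. At 1 v 8% the 10-year incidence is 9.1% v 6.6%.
- *That progression found on a rescan after discharge is discarded.* Section 3.10.1 does not say how such patients are coded, and Appendix 1 can return them to active monitoring.
- *That the validation as a whole is biased.* Calibration uses Kaplan-Meier, and the Brier score, C-statistic, D-statistic and AUC are versions for censored data. The coding rule does not reach them.

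**Conclusion.** The point holds for the PS/ACCI progression analysis and for what is built on it: the comparison with the training data and Stage 4. The downward direction is certain from the definition of cumulative incidence and from the protocol's own statement about progression after discharge. The size is not known. Under constant hazards and an assumed 10% to 70% discharged or lost by 5 years, a true 10% risk is reported as 9.0% down to 3.9%. With equal progression hazards and a 10% risk, the false-positive rate runs from about 5-6% with equal discharge to about 80-90% with very unequal discharge; at a 20% risk the upper end approaches 100%. The good behaviour of censoring in these runs assumes that discharge is independent of progression, which the documents do not establish.

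**What to change.** Revise the progression paragraph of section 3.10.1; section 3.10.3 already schedules a review of the analysis plan before the final analysis.

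1. **Primary progression analysis.** Treat only death during follow-up (not counted as progression) and intervention before progression as competing. Censor discharged or lost patients at their last scan or assessment. Use inverse-probability-of-censoring weights on imaging risk group, PS and ACCI, because discharge may be informative.
2. **Add a cause-specific hazard comparison** across PS/ACCI groups, because cumulative incidence also reflects differing mortality.
3. **Report discharge and loss by PS/ACCI**, including patients discharged at the first management decision, who contribute little or no follow-up under censoring.
4. **Keep the present coding as a secondary analysis**, labelled *progression detected before monitoring ended*, for comparison with the training data.
5. **Do not extend follow-up only for rescanned patients in the primary analysis.** Section 3.8.3 selects rescans by suspected relation to the meningioma. In a simulation assuming that 60% of later progressors and 5-10% of other discharged patients are rescanned, that rule gave 17-18% against a true 9.1% at 20% discharge per year, and 10.4-10.5% at 5% per year. Plain censoring recovered 9.1% when discharge was independent of progression. Use the rescan data in a labelled sensitivity analysis only.

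The cost is one reworded paragraph and a few extra analyses on data already being collected. The downsides are wider intervals late in follow-up, reliance on the censoring model, and a primary curve that may not match the training curves directly, which is why item 4 is kept.

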3.4. Sample size

For external validation studies, a minimum of 100 events is required (12). The risk of incidental meningioma progression is estimated to be 10% (11). Based on this, data for 1000 patients will be required. To account for variability in the progression risk, follow-up regimes and loss to follow-up, we will include a minimum of 1500 patients across participating centres.

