3.6. Data collection

Data will be collected at each centre by members of the local team. Data will be collected from the patient's medical records and MRI scans. All clinical and radiological information collected for this study by the local investigators should be available routinely and no extra patient assessment will be required. Data will be collected and stored online through a secure University of Liverpool server running the Research Electronic Data Capture (REDCap) web application and using the patient unique study number. Local investigators will be given secure REDCap project server login details. No patient identifiable information will be uploaded or stored on the REDCap database. The study number (site ID_patient ID) is generated by REDCap on creating a new patient record in the database. The clinical team can only view the records of patients from their own centre. All local investigators will store a copy of the link between the patient's unique study number and their patient identifiers on a secure password protected computer, using a blank link file provided by the study team.

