3.10.2. Model recalibration

If calibration and discrimination measures of external validation demonstrate a poor fit, the model will be recalibrated and adjusted using the data of included patients. This will be done over four stages:

- Stage 1: The regression coefficients (including the intercept and slope) will be recalibrated. This will be done using a logistic regression model fitted with the linear predictor as the only covariate.
- Stage 2: The recalibrated model predictors will each be removed in a stepwise manner by a non-automated criterion-based procedure starting with the variable with a hazard ratio closest to 1. After removal of this variable, the aforementioned measures of discrimination of calibration and discrimination will be reassessed to detect model improvement. If the performance of the model is unimproved or worsens, the variable will be reintroduced to the model. This step will be repeated in a staged manner until no further improvements are detected. Introduction of new predictive variables will not be possible as data points captured in this study have been limited to predictive parameters and outcomes as per the IMPACT model.
- Stage 3: The internal validity of the updated model will be assessed using a bootstrapping method
- Stage 4: Adjusted stratification by ACCI and PS (Table 1) will be performed to achieve statistically significant differences in equality across cumulative incidence rate groups, judged by the Fine and Gray test

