3.10.3. Additional analyses

We envisage that imaging protocols in the participating centres are varied and non-standardised and thus, the growth rate for each meningioma will be determined using a joint longitudinal and event-time outcomes model which does not require regularly spaced time points, and adjusts for informative follow-up, assuming a different intercept and slope for each meningioma (25, 26). The sum of the regression coefficients of random and fixed effects for the slope estimated from the linear model will best represent the average growth rate for each meningioma. Absolute growth rate (AGR) will be defined as the increase in volume per year in cm³ whereas relative growth rate (RGR) will be defined as the percentage increase in volume per year.

Demographic differences across management and outcome groups will be explored with the χ^2 test for categorical variable and the Mann-Whitney U test or Student's t-test for continuous variables. Correlation between baseline variables will be evaluated using the Pearson correlation coefficient. Normally distributed continuous variables will be expressed as mean (standard deviation [SD]) whereas skewed variables as median (interquartile range [IQR]). Differences will be considered statistically significant at $P < 0.05$.

This statistical analysis plan will be reviewed prior to the final analysis of the study.

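### Section 3.10 makes no allowance for centre in an international multicentre cohort, so its 95% intervals will be too narrow if progression risk varies by centre, by an amount the protocol does not let us fix.

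*Protocol*

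**What the plan says.** The primary objective (Protocol 2.1) is external validation of IMPACT in a retrospective, international, multicentre cohort (3.1). Section 3.4 sets the size: "we will include a minimum of 1500 patients across participating centres".

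Section 3.10.1 plans calibration, a Brier score and discrimination measures, then two competing risk analyses, one for intervention and one for disease progression. On the comparison of patient groups it says: "To test the equality across CIR groups, the Fine and Gray test will be carried out". On the comparison with the development cohort it says: "Plots of CIRs and 95% confidence intervals (CIs) will also be generated and compared to the training data set (11"). If the fit is poor, section 3.10.2 updates the model, and Stage 3 reads: "The internal validity of the updated model will be assessed using a bootstrapping method".

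Section 3.10 contains no centre term, centre stratification, clustered variance or measure of heterogeneity between centres. Its only random effects are an intercept and slope per meningioma, in the growth model. Section 3.10.3 nevertheless expects that "imaging protocols in the participating centres are varied and non-standardised". Centre is available as a variable, because section 3.6 states: "The study number (site ID_patient ID) is generated by REDCap" when a record is created.

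**The concern.** Several parts of the endpoint definitions make it plausible that observed risk differs between centres for reasons unrelated to the tumour:

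- Most components of progression (3.5.1) are read from scans, so when and whether progression is detected depends on the local scanning schedule. Local teams collect the data from the scans (3.6).
- In the progression analysis (3.10.1), discharge, loss to follow-up and intervention before progression are competing events. Local discharge and treatment policy therefore feeds directly into the CIR.
- The other CIR is for primary intervention, which is itself a local decision.

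If centres differ, patients from one centre resemble each other, and an interval computed as if all patients were independent is too narrow. Readers will judge agreement with the training data by those intervals. Section 3.10.2 also makes model updating depend on the overall fit, so misjudged precision could affect that decision.

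A second problem does not depend on the variance. A single calibration plot and a single C-statistic cannot show whether IMPACT performs well in some settings and badly in others, which is a main reason for validating internationally.

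**Working it through.** **Inputs from the Protocol (3.4).** "For external validation studies, a minimum of 100 events is required (12"). "The risk of incidental meningioma progression is estimated to be 10% (11"). The minimum sample is 1500.

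**The plan's own figure.** 100 / 0.10 = 1000 patients, which reproduces. At 1500 patients and 10% risk, the expected number of events is 1500 × 0.10 = 150. The step from 1000 to 1500 is attributed to variability in risk, follow-up regimes and loss to follow-up. No centre design effect is named.

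**Assumptions, not in the Protocol.** The number of centres K, the ICC and equal centre sizes. A simple 10% proportion stands in for the CIR.

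**Interval for the whole cohort, ignoring centre.** Half-width = 1.96 × √(0.10 × 0.90 / 1500) = 1.52 percentage points.

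**Allowing for centre.** Design effect DE = 1 + (m − 1) × ICC, with m = 1500/K. The interval should be √DE times as wide.

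| K | m | DE, ICC 0.01 | √DE | DE, ICC 0.05 | √DE |
|---|---|---|---|---|---|
| 10 | 150 | 2.49 | 1.58 | 8.45 | 2.91 |
| 30 | 50 | 1.49 | 1.22 | 3.45 | 1.86 |
| 50 | 30 | 1.29 | 1.14 | 2.45 | 1.57 |
| 100 | 15 | 1.14 | 1.07 | 1.70 | 1.30 |

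With 30 centres the half-width rises from 1.52 to 1.52 × 1.22 = 1.85 points at ICC 0.01, and to 1.52 × 1.86 = 2.83 points at ICC 0.05. Unequal centre sizes increase the design effect: at K = 30 and ICC 0.05, a coefficient of variation of 0.8 in centre size raises DE from 3.45 to 5.05.

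**What these ICCs mean.** ICC = SD² / (p(1 − p)). A between-centre SD of 3 points around 10% gives 0.03² / 0.09 = 0.01. An ICC of 0.05 corresponds to an SD of √(0.05 × 0.09) = 6.7 points.

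**Within strata.** Two PS categories and three ACCI groups, if crossed into equal cells, give 1500 / 6 = 250 patients per cell. With 30 centres, m = 8.33. DE is 1.07 at ICC 0.01 (interval 1.04 times as wide) and 1.37 at ICC 0.05 (1.17 times).

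**Fine and Gray test.** This compares patient groups inside the cohort, so shared centre effects largely cancel. A beta-binomial simulation (30 centres of 50, 20,000 runs, no true group effect, a two-proportion test standing in for Fine and Gray) gave these rejection rates at a nominal 5%:

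- Groups balanced within centres: 4.5% to 4.9%.
- Group mix uneven between centres: 6.0%, 7.2% and 10.7% at ICC 0.01, 0.02 and 0.05.

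In a separate simulation of 4,000 runs, with PS mix varying by centre, a centre-stratified Mantel-Haenszel test stayed at 4% to 5%. The pooled test ran from 5% to 19%, exceeding 10% only with strong case-mix variation.

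**The case against.** A reader might infer that the comparison with the training set would reject at several times 5%. The documents do not support that, for three reasons.

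- Section 3.10.1 plans a comparison of plots. No test, P value or decision rule is attached to it.
- If one imagines testing the overall risk against a fixed training value, the error is 2 × (1 − Φ(1.96/√DE)). That runs from 5.2% (K = 100, ICC 0.001) to 50% (K = 10, ICC 0.05), so the figure depends on inputs that the Protocol does not give.
- The training estimate has its own sampling error. Assuming 200 to 800 unclustered training patients and K = 20 to 50, the error is 5.4% to 8.0% at ICC 0.01 and 7.0% to 19.5% at ICC 0.05. It is larger (24% to 44% at ICC 0.01) only if the training set is treated as one cluster.

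Other points against the concern also carry weight. Section 3.4 mentions variability in risk without saying that it lies between centres. The imaging remark in 3.10.3 comes with a response, a joint model that copes with irregular scan times, though that model concerns growth rates and not the CIR intervals. The video manual (3.8.2) and the compulsory assessment (3.9) should reduce differences in reading, but they do not touch scanning, discharge or treatment policy. Section 3.10 is silent on the variance method and the resampling unit; it does not affirm independence. A separate analysis plan may settle these points, although 3.10.3 describes its own text as the statistical analysis plan. Finally, at about 150 events, 30 to 40 centres would have roughly 4 to 5 events each, so a C-statistic for every centre is not workable.

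**Conclusion.** The point holds as a conditional one about precision and transportability. The written plan makes no allowance for centre, the Protocol itself gives reasons to expect centres to differ, and intervals that ignore this are too narrow if risk does vary.

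The size cannot be fixed from the document. Over the tabulated range, the overall interval should be between about 1.07 and 2.9 times as wide. At 30 equal centres the factor is about 1.2 (ICC 0.01) to 1.9 (ICC 0.05), and within PS/ACCI strata it is much smaller. These figures assume that the results are meant to apply beyond the particular centres that take part, which is the natural reading of an external validation but is not stated. The Fine and Gray test is affected only if PS or ACCI mix differs between centres. The inability of one pooled result to show variation in performance does not depend on the ICC.

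This is an inexpensive improvement that should be made before the final analysis.

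**What to change.** Using the site ID in the study number:

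1. Obtain intervals for the CIRs and for the calibration and discrimination measures by a bootstrap that resamples centres, or by cluster-robust variance. Resample centres in Stage 3 of 3.10.2 as well.
2. Stratify the Fine and Gray test by centre, or by country or region where centres are small, at least as a sensitivity analysis.
3. Report the observed/expected ratio and C-statistic by country or by grouped centres, with a summary of heterogeneity between groups. Do not attempt this for each small centre.
4. Report the number and size of centres, so that readers can judge the effect.

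The cost is analysis wording and code. No new data are needed, and 3.10.3 already schedules a review of the plan before the final analysis. The downside is wider intervals and a rule, set in advance, for grouping small centres.
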